Appendix 1: Schedule of Activities

	Screening		Treatment Per	iod	Treatment		
Assessment	Days -28 to -1	Baseline (Week 1)	Q2W (±3 days) for the First 12 Weeks ^h	Q4W thereafter until PD, Death, or Withdrawal from Study ^a (±3 days)	Discontinuation Visit (28 days after Final Dose of Study Drug [±5 days])	Off-Tx Visits ⁵	Long- Term Follow- Up °
Additional mandatory laboratory assessments ^h			x				
Plasma PK sample (2 mL) ⁱ		х		x			
Plasma sample for biomarkers (10 mL) ^j		х		Only at Week 8, Week 36, and at progression			
Tumor tissue sample ^k	x	х					
Pregnancy test	X ^m	X ⁿ		Urine pregnancy test Q4W and as clinically indicated	x		
Alectinib dispensing		х		x			
Disease assessment (CT scans)	x			Q8W (±5 days)		Q8W (± 5 days)	
MRI or CT scan of the brain °	х			X ^p		X p	
Radionuclide bone scan ^q	х						
Concomitant medications	х	х		x	x		
Adverse events	x	x		x	x		
Patient-reported outcomes r		x		x	x		
Subsequent therapy and SFU							x

Appendix 1: Schedule of Activities

CPK = creatine phosphokinase; CT = computed tomography (scan); eCRF = electronic Case Report Form; ECOG = Eastern Cooperative Oncology Group; FFPE = formalin fixed, paraffin embedded; FMI = Foundation Medicine, Inc.; GGT = gamma-glutamyl transferase; MRI = magnetic resonance imaging; NA = not applicable; NGS = next-generation sequencing; PD = progressive disease; PK = pharmacokinetic; PRO = patient-reported outcome; Q2W = every 2 weeks; Q4W = every 4 weeks; Q8W = every 8 weeks; RBR = Research Biosample Repository; SFU = survival follow-up; Tx = treatment; WES = whole exome sequencing; WGS = whole genome sequencing.

Notes: Results of laboratory tests and ECG performed within 3 days before first dose of study drug can be used as baseline assessments.

- ^a Treatment beyond radiological progression is possible in the event of isolated lesion progression if in the investigator's opinion there is evidence of ongoing clinical benefit. For patient receiving study drug beyond radiological progression, scheduled visits (including disease assessments) will continued to be performed until treatment discontinuation.
- ^b For patients who discontinue study treatment prematurely for reasons other than disease progression, tumor assessments should continue until progression.
- c Required follow-up information (e.g., survival status and information on further cancer therapies and procedures [radiotherapy, surgery]) will be collected via telephone calls every 3 months (±14 days) until death, loss to follow-up, or study termination by the Sponsor. More frequent calls may be required when clinical data cut-offs are performed.
- ^d Complete physical examination (head, eyes, ears, nose, and throat, and the cardiovascular, dermatologic, musculoskeletal, respiratory, gastrointestinal, genitourinary, and neurologic systems). Baseline and post-baseline visits: limited physical examination, symptom-directed, and as clinically indicated. For patients with primary CNS tumors, a neurological examination must be performed at each tumor assessment visit and compared with the neurological examination performed at the time of the last disease assessment.
- ^e Coagulation includes PT (or INR) and aPTT (or PTT).
- ^f Includes WBC count, RBC count, hemoglobin, hematocrit, platelet count, and differential count (neutrophils, eosinophils, basophils, monocytes, lymphocytes).
- ^g Includes sodium, potassium, chloride, glucose, creatinine, creatinine clearance (calculated according to the method of Cockcroft and Gault), GGT, total protein, albumin, phosphorus, magnesium, calcium, total and direct bilirubin, ALP, CPK, ALT, AST, uric acid, BUN, or urea.
- ^h Additional mandatory laboratory assessments include CPK at 2 weeks after baseline and liver enzymes (ALT, AST, ALP, and total and direct bilirubin) 2, 6, 10, and 12 weeks after baseline. These are in addition to the regular assessments performed Q4W.
- ⁱ Plasma sample for PK to be taken during screening or before first dose of study drug at baseline. At subsequent visits, time of sample draw and last dose of alectinib must be captured. See Appendix 2 for details.
- ^j See Appendix 2 for details.
- ^k Available (most recent) FFPE tissue block or 11 unstained slides 4–5 μm thick. Tissue sample is not required if ALK positivity was determined by FMI using tissue. A tissue block or 11 unstained slides are also required for all patients who have local ALK-positive test by NGS.
- ¹ Tumor tissue sample for prospective testing at FMI if local ALK test result is not acceptable for enrollment as specified by the protocol.

Alectinib—F. Hoffmann-La Roche Ltd

117/Protocol BO41929, Version 4

Appendix 1: Schedule of Activities

- ^m During screening, a negative serum pregnancy test must be obtained.
- ⁿ At baseline a negative urine pregnancy test must be obtained before first dose of study drug is administered (unless a negative serum test was obtained within 10 days of first dose of study drug).
- For primary CNS tumors, at all tumor assessment visits, corticosteroid use for CNS disease must be compared with the corticosteroid intake at the time of the last disease assessment. Changes in corticosteroid dose for reasons other than for CNS tumor control do not need to be taken into consideration when making this comparison.
- ^p As clinically indicated (mandatory Q8W [±5 days] for primary CNS tumors or for patients with CNS metastases at baseline).
- ^q A radionuclide bone scan is required at screening for patients with known or suspected bone metastasis.
- ^r The PRO questionnaires QLQ-C30 and EQ-5D-5L will be completed by patients at home during the scheduled visits performed by the mobile health care professional. Questionnaires are to be completed before any other visit-related assessment is performed.

Appendix 2 Schedule of Pharmacokinetic and Biomarker Samples

Table 1 Pharmacokinetic Schedule of Activities

Visit	Timepoint	Sample Type
Baseline (Week1)	Predose	Plasma
Week 4 and every 4 weeks thereafter during the treatment period	Record time: drawn plasma and last dose of alectinib	Plasma

Table 2 Biomarker Schedule of Activities

Visit	Sample Type
Screening	Available (most recent) tumor tissue ^a
Baseline (Week 1) ^b	Plasma for biomarkers
Week 8	Plasma for biomarkers
Week 36	Plasma for biomarkers
Disease progression [◦]	Plasma for biomarkers

ALK = anaplastic lymphoma kinase; FMI = Foundation Medicine, Inc.

- ^a Not necessary if ALK positivity was already determined by FMI on tissue. It includes patients identified outside FMI Precision Enrollment. Plasma may be acceptable after consultation with the Medical Monitor.
- ^b Sample to be collected predose.
- ^c Plasma for disease progression biomarker will be collected within 30 days of disease progression per investigator's assessment according to Response Evaluation Criteria in Solid Tumors, Version 1.1 or, for patients with primary CNS tumors, Response Assessment in Neuro-Oncology criteria.

ANAPLASTIC LYMPHOMA KINASE (ALK)–POSITIVE TESTS AND REQUIREMENTS FOR TISSUE

Data generated may support possible registration of tissue and plasma next-generation sequencing assays as a companion diagnostic for alectinib across tumor types.

The tests for determination of ALK positivity and tissue requirements are presented in Table 3.

Table 3 ALK-Positive Tests and Tissue Requirements

ALK-Positive Result on	Tumor Tissue Sample	Retrospective Testing
F1CDx	Not applicable	—
F1LiquidCDx	Required	F1CDx
F1HEME	Required	F1CDx
Local NGS testing except FMI F1CDx ^{a, b}	Required	F1CDx

ALK = anaplastic lymphoma kinase; CDx = companion diagnostic; F1 = Foundation One; FMI = Foundation Medicine, Inc.; NGS = next-generation sequencing.

^a If tissue is not available, blood may be acceptable after consultation with the Medical Monitor.

^b If local NGS test is from FMI but is not listed in the table, tissue is also required.

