2.4 EXPLORATORY BIOMARKER OBJECTIVES

The exploratory biomarker objectives for this study are as follows:

- To identify and/or evaluate biomarkers that are associated with primary or acquired resistance to alectinib in the biomarker-evaluable population by analyzing the relationship between biomarkers found in circulating DNA in blood and tumor tissue, with efficacy endpoints
- To assess relationship between levels of circulating free DNA (cfDNA) at baseline and changes in levels of cfDNA at different timepoints during treatment with efficacy endpoints

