An interim, non-binding analysis will be performed once the first 15 RECIST v1.1 investigator-assessed response-evaluable patients with ALK fusions (excluding patients with primary CNS tumors and patients with CUP) have a response evaluation at 8 weeks available (unless they progressed or discontinued earlier from the study). If the analysis result shows that the response rate does not achieve at least 25% (4 responders), the study may be terminated due to futility.

Patients will receive alectinib at the dose of 600 mg BID, taken with food, until disease progression, death, or withdrawal for any other reasons. Treatment beyond radiological progression is possible in the event of isolated lesion progression if, in the investigator's opinion, there is evidence of ongoing clinical benefit.

All enrolled patients will undergo regular, scheduled visits until disease progression, death, withdrawal from the study, or study termination, whichever occurs first. For patients receiving alectinib beyond radiological progression, scheduled visits (including tumor assessments), will continue to be performed until treatment permanently discontinues.

For the first 12 weeks (3 months), regular safety assessments will be scheduled at baseline and every 2 weeks to allow for more frequent liver function and CPK assessments as per alectinib label. After Week 12, patients will undergo regular safety visits every 4 weeks. See Appendix 1 for the schedule of activities.

Tumor assessments will be performed during screening and every 8 weeks (calculated from baseline) during study conduct and will consist of computed tomography (CT) and brain magnetic resonance imaging (MRI) scans (or brain CT scans if MRI is not feasible). Brain scans will be mandatory at baseline and during study conduct for patients with primary CNS tumors or brain metastases at baseline. For patients without brain metastases at baseline, brain scans will be performed as clinically indicated during study conduct. A safety follow-up will occur during the treatment discontinuation visit 28 days (4 weeks) after the final dose of alectinib.

Plasma samples will be obtained for biomarker analysis at baseline, Week 8, Week 36, and upon disease progression, and for PK analysis at baseline and every 4 weeks at scheduled visits during the treatment period.

Figure 1 presents an overview of the study design. The schedule of activities is provided in Appendix 1.
Figure 1 Study Schema

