3.3.4 Rationale for Biomarker Assessments

Cancer is a heterogeneous disease, and ALK-positive tumors as defined in this study can occur in different forms, depending on the type of ALK fusion partner or ALK-activating mutation driving the malignancy (Hallberg and Palmer 2013). ALK fusion partners, ALK fusion variants, and ALK mutations, or mutations in tumor-related genes occurring before or during alectinib treatment may influence treatment efficacy. ALK mutations and mutations in cancer-related genes can appear as a result of biologic selection pressure on tumor cells induced by the treatment. Therefore, patients enrolled in the study may not be equally likely to benefit from treatment with alectinib. Biomarker samples collected prior to dosing will be assessed in an effort to identify those patients most likely to respond to alectinib. Biomarker samples collected during study conduct will be assessed to investigate possible correlation between levels of cfDNA with activity of alectinib or progression during treatment, and samples collected at progression will be analyzed in an effort to identify acquired resistance mechanisms to alectinib.

Alectinib—F. Hoffmann-La Roche Ltd 40/Protocol BO41929, Version 4

Validated and approved diagnostic tests are required to identify patients with ALK-positive tumors who are eligible for alectinib treatment across tumor types. Currently available companion diagnostic tests for alectinib are approved only for NSCLC. Therefore, approved tissue and plasma NGS assays to detect ALK-positive patients for alectinib treatment across tumor types are needed. Patients may not have enough tumor tissue available to be tested for rare biomarkers such as ALK by tissue. Plasma ALK assays that analyze circulating tumor nucleic acids will enable more patients to be tested for ALK positivity. Data generated in this study may support a possible registration of tissue and plasma NGS assays as CDx for alectinib across tumor types.

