Use of the following concomitant therapies (e.g., prescription drugs, over-the-counter drugs, herbal or homeopathic remedies, and nutritional supplements) is prohibited during the study except during follow-up period and for at least 14 days prior to initiation of alectinib treatment, unless otherwise specified. Exceptions to restrictions of the therapies listed below may be made if the rationale is discussed and documented between the investigator and Sponsor's clinical pharmacologist:

• Systemic immunosuppressive drugs, cytotoxic or chemotherapeutic agents

Note: The use of systemic corticosteroids for the management of CNS metastases may be permitted after discussion with the Medical Monitor.

• Additional investigational drug (excluding post-progression during survival follow-up)

- Radiotherapy/radionuclide therapy, except for palliative radiotherapy to bone lesions or for pain control
- If palliative radiation is indicated, alectinib should be interrupted for at least 24 hours before start of radiation treatment

Dosing of alectinib may resume with the resolution of any radiation toxicity to Grade 1 or better.

The list of medication provided above is not necessarily comprehensive. If in doubt, the investigator may consult with the Medical Monitor when prescribing concomitant medications.

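### The progression plasma sample may be drawn up to 30 days after progression with no requirement that it precede the next anti-cancer therapy, so a compliant sample could partly reflect the new drug

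*Protocol*

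**What the plan says.** The exploratory biomarker objective in Protocol Section 2.4 includes finding "biomarkers that are associated with primary or acquired resistance to alectinib in the biomarker-evaluable population". Section 3.3.4 gives the purpose of the late sample: "samples collected at progression will be analyzed in an effort to identify acquired resistance mechanisms to alectinib".

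The timing of that sample appears in three forms:

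- Section 3.1, and the synopsis in the same terms: "Plasma samples will be obtained for biomarker analysis at baseline, Week 8, Week 36, and upon disease progression".
- Appendix 1, biomarker plasma row, treatment-period column: "Only at Week 8, Week 36, and at progression". The row has no entry under the treatment discontinuation visit.
- Appendix 2, Table 2, footnote c: "Plasma for disease progression biomarker will be collected within 30 days of disease progression", as assessed by the investigator under RECIST v1.1 or, for primary CNS tumors, RANO.

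The baseline sample in the same table carries a rule relative to drug intake: "Sample to be collected predose". The progression sample carries none. SAP Section 5.7.4 repeats the protocol's biomarker text and adds no rule on when this sample must be drawn or how a late one is handled.

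**The concern.** The sample is meant to show what the tumor looked like when it escaped alectinib. Section 3.3.4 itself says that mutations can emerge because treatment exerts selection pressure on tumor cells. By the same reasoning, stopping alectinib or starting another drug can change what is found in plasma. If the blood is drawn after the next therapy has begun, part of the signal may belong to that therapy.

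At stake is the reading of a small set of specimens. The primary population is about 50 patients, and Appendix 2 schedules plasma as the only specimen at progression; tumor tissue is scheduled at screening only. A sample drawn too late cannot be drawn again.

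**Working it through.** The plan states no figure for this point, so there is none to reproduce. The check sets the relevant provisions side by side.

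| Question | Where | What it provides |
|---|---|---|
| When is the sample drawn? | Protocol 3.1, Appendix 1 | At progression |
| What tolerance applies? | Appendix 2, Table 2, footnote c | 30 days around investigator-assessed progression |
| Must it precede the next therapy? | Protocol and SAP | No such requirement found |
| Is other therapy possible by then? | Protocol 4.5.3 | Use of the listed therapies "is prohibited during the study except during follow-up period" |
| Can it start soon after alectinib? | Protocol 6.5 | The unrelated-adverse-event summary closes 28 days after the last dose, or sooner if another anti-cancer therapy starts |
| Is the next therapy recorded? | Protocol 4.7.1, Appendix 1 | Yes, at three-monthly follow-up; not linked to the draw |
| Is a late sample handled in analysis? | SAP 5.7.4, SAP Table 4 | No flag, separation or exclusion; the biomarker-evaluable population is not defined |

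**Step 1.** Footnote c is the only place that gives the draw a numerical window. A draw on day 25 after progression complies with it.

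**Step 2.** Section 6.5 provides for a new therapy inside 28 days of the last dose. If alectinib stops at or near progression, those 28 days and the 30-day window largely overlap.

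**Step 3.** Both events can therefore fall inside the window, and no provision fixes their order. The draw may follow the new therapy without any protocol deviation.

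**Step 4.** To show how much of the window is exposed, let d be the number of days from progression to the first dose of the next therapy. The documents do not give d, so these values are assumptions. The part of the 30 days after progression in which a draw would fall on the new therapy is 30 − d, and zero once d reaches 30:

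- d = 7: 30 − 7 = 23 days
- d = 14: 30 − 14 = 16 days
- d = 21: 30 − 21 = 9 days
- d = 28: 30 − 28 = 2 days

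These are lengths of permitted time. They are not probabilities, because the documents say nothing about when within the window draws will be made.

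**The case against.** The best defence is that the plan intends a draw at progression and that 30 days is only an outer tolerance. Section 3.1 and Appendix 1 read that way. The tolerance also has an evident practical basis: scans are done at a local imaging facility, blood is drawn by a visiting professional at home, and after Week 12 the home visits are four weeks apart. The footnote gives no direction, so a draw shortly before documented progression also fits. Patients treated beyond radiological progression may still be on alectinib at the draw. Subsequent therapies are collected and summarised (SAP Section 5.7.2), so affected samples could be identified afterwards if draw dates are held. Section 4.6.6 refers sampling procedures to a laboratory manual that was not available here and may contain a timing rule.

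All of this stands and limits the point. It does not remove it: the stated window is what staff will follow, and none of these provisions puts the draw before the next drug.

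Three stronger readings are tempting and are not supported:

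- A reader might infer that the sample is planned for the discontinuation visit, four weeks after the last dose. Appendix 1 has no biomarker plasma entry at that visit.
- A reader might want to state what share of samples would be lost. The documents give no number of progressions, no timing of next therapy and no distribution of draw dates. Harm needs both an early switch and a late draw in the same patient, so the share switching early would not be the answer even if it were known.
- A reader might call late samples uninterpretable, or the analysis biased. Section 3.3.4 supports a possible change under treatment but gives no time scale or size for it.

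**Conclusion.** The point holds as a modest, inexpensive improvement. The protocol permits the only scheduled progression specimen to be drawn after a new anti-cancer therapy has begun, and the SAP has no rule for recognising or handling such a sample. Its frequency and effect are unknown from the documents.

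The reach is limited to the exploratory resistance analysis, which is to be communicated outside the main Clinical Study Report.

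The conclusion rests on two assumptions: that the laboratory manual does not already impose a rule, and that at least some patients stop alectinib near progression and move to another therapy within the window.

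**What to change.** Amend Appendix 2, Table 2, footnote c so that the plasma is collected *at progression, or within 30 days of it, and before the first dose of any subsequent anti-cancer therapy*. State that this moves the blood draw and must not delay treatment. Carry the same clause into the laboratory manual.

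Record the draw date alongside the date of the last alectinib dose and the start date of the next therapy. In SAP Section 5.7.4, state that samples drawn after a new therapy will be flagged and reported separately or in a sensitivity analysis. Excluding them would discard data in a rare population, and flagging is enough. The flag also covers patients who stop alectinib before progression and have already started another therapy when they progress, for whom the new clause cannot be met.

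The cost is one clause in the protocol and the manual, one date to record if it is not already held, and one sentence in the SAP. The downside is that some home visits must be scheduled earlier.

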Appendix 3 ECOG Performance Status Scale

Grade	ECOG Performance Status
0	Fully active, able to carry on all pre-disease performance without restriction
1	Restricted in physically strenuous activity but ambulatory and able to carry out work of a light or sedentary nature, e.g., light house work, office work
2	Ambulatory and capable of all self-care but unable to carry out any work activities; up and about more than 50% of waking hours
3	Capable of only limited self-care; confined to bed or chair more than 50% of waking hours
4	Completely disabled; cannot carry on any self-care; totally confined to bed or chair
5	Dead

Appendix 4 List of P-gp Substrates

This representative list is not intended to be an exhaustive list. Each patient's concomitant medications should be carefully considered by the investigator with regard to the benefit–risk assessment for the particular patient and appropriate monitoring, including any concomitant medication, dose adjustment, or therapeutic alternatives, which should be determined by the investigator caring for the patient.

P-gp Substrates

aliskiren, ambrisentan, colchicine, dabigatran, digoxin, everolimus, fexofenadine, imatinib, lapatinib, maraviroc, nilotinib, posaconazole, pravastatin, ranolazine, saxagliptin, sirolimus, sitagliptin, talinolol, tolvaptan, topotecan

P-gp=P-glycoprotein.

For additional information, please refer to:

http://www.fda.gov/Drugs/DevelopmentApprovalProcess/DevelopmentResources/DrugIn teractionsLabeling/ucm080499.htm

Appendix 5 Response Evaluation Criteria in Solid Tumors, Version 1.1 (RECIST v1.1)

Selected sections from the Response Evaluation Criteria in Solid Tumors, Version 1.1 (RECIST v1.1) (Eisenhauer et al. 2009; Schwartz et al. 2016), are presented below, with slight modifications from the original publication and the addition of explanatory text as needed for clarity.¹

TUMOR MEASURABILITY

At baseline, tumor lesions/lymph nodes will be categorized as measurable or non-measurable as described below. All measurable and non-measurable lesions should be assessed at screening and at subsequent protocol-specified tumor assessment timepoints. Additional assessments may be performed as clinically indicated for suspicion of progression.

DEFINITION OF MEASURABLE LESIONS

Tumor Lesions

Tumor lesions must be accurately measured in at least one dimension (longest diameter in the plane of measurement is to be recorded) with a minimum size as follows:

- 10 mm by computed tomography (CT) or magnetic resonance imaging (MRI) scan (CT/MRI scan slice thickness/interval ≤5 mm)
- 10-mm caliper measurement by clinical examination (lesions that cannot be accurately measured with calipers should be recorded as non-measurable)
- 20 mm by chest X-ray

Malignant Lymph Nodes

To be considered pathologically enlarged and measurable, a lymph node must be \geq 15 mm in the short axis when assessed by CT scan (CT scan slice thickness recommended to be \leq 5 mm). At baseline and follow-up, only the short axis will be measured and followed. Additional information on lymph node measurement is provided below (see "Identification of Target and Non-Target Lesions" and "Calculation of Sum of Diameters").

¹ For consistency within this document, the section numbers and cross-references to other sections within the article have been deleted and minor formatting changes have been made.

DEFINITION OF NON-MEASURABLE LESIONS

Non-measurable tumor lesions encompass small lesions (longest diameter < 10 mm or pathological lymph nodes with short axis \geq 10 mm but < 15 mm) as well as truly non-measurable lesions. Lesions considered truly non-measurable include leptomeningeal disease, ascites, pleural or pericardial effusion, inflammatory breast disease, lymphangitic involvement of skin or lung, peritoneal spread, and abdominal mass/abdominal organomegaly identified by physical examination that is not measurable by reproducible imaging techniques.

SPECIAL CONSIDERATIONS REGARDING LESION MEASURABILITY

Bone lesions, cystic lesions, and lesions previously treated with local therapy require particular comment, as outlined below.

Bone Lesions:

- Technetium-99m bone scans, sodium fluoride PET scans, and plain films are not considered adequate imaging techniques for measuring bone lesions. However, these techniques can be used to confirm the presence or disappearance of bone lesions.
- Lytic bone lesions or mixed lytic-blastic lesions with identifiable soft tissue components that can be evaluated by cross-sectional imaging techniques such as CT or MRI can be considered measurable lesions if the soft tissue component meets the definition of measurability described above.
- Blastic bone lesions are non-measurable.

Cystic Lesions:

- Lesions that meet the criteria for radiographically defined simple cysts should not be considered malignant lesions (neither measurable nor non-measurable) since they are, by definition, simple cysts.
- Cystic lesions thought to represent cystic metastases can be considered measurable lesions if they meet the definition of measurability described above. However, if non-cystic lesions are present in the same patient, these are preferred for selection as target lesions.

Lesions with Prior Local Treatment:

• Tumor lesions situated in a previously irradiated area or in an area subjected to other loco-regional therapy are usually not considered measurable unless there has been demonstrated progression in the lesion.

METHODS FOR ASSESSING LESIONS

All measurements should be recorded in metric notation, using calipers if clinically assessed. All baseline evaluations should be performed as close as possible to the treatment start and never more than 4 weeks before the beginning of the treatment.

The same method of assessment and the same technique should be used to characterize each identified and reported lesion at baseline and during the study. Imaging-based evaluation should always be the preferred option.

CLINICAL LESIONS

Clinical lesions will only be considered measurable when they are superficial and \geq 10 mm in diameter as assessed using calipers (e.g., skin nodules). For the case of skin lesions, documentation by color photography, including a ruler to estimate the size of the lesion, is suggested.

CHEST X-RAY

Chest CT is preferred over chest X-ray, particularly when progression is an important endpoint, since CT is more sensitive than X-ray, particularly in identifying new lesions. However, lesions on chest X-ray may be considered measurable if they are clearly defined and surrounded by aerated lung.

CT AND MRI SCANS

CT is the best currently available and reproducible method to measure lesions selected for response assessment. In this guideline, the definition of measurability of lesions on CT scan is based on the assumption that CT slice thickness is ≤ 5 mm. When CT scans have slice thickness of >5 mm, the minimum size for a measurable lesion should be twice the slice thickness. MRI is also acceptable.

If prior to enrollment it is known that a patient is unable to undergo CT scans with intravenous (IV) contrast because of allergy or renal insufficiency, the decision as to whether a non-contrast CT or MRI (without IV contrast) will be used to evaluate the patient at baseline and during the study should be guided by the tumor type under investigation and the anatomic location of the disease. For patients who develop contraindications to contrast after baseline contrast CT is done, the decision as to whether non-contrast CT or MRI (enhanced or non-enhanced) will be performed should also be based on the tumor type and the anatomic location of the disease, and should be optimized to allow for comparison with prior studies, if possible. Each case should be discussed with the radiologist to determine if substitution of these other approaches is possible and, if not, the patient should be considered not-evaluable from that point forward. Care must be taken in measurement of target lesions and interpretation of

non-target disease or new lesions on a different modality, since the same lesion may appear to have a different size using a new modality.

ENDOSCOPY, LAPAROSCOPY, ULTRASOUND, TUMOR MARKERS, CYTOLOGY, HISTOLOGY

Endoscopy, laparoscopy, ultrasound, tumor markers, cytology, and histology cannot be utilized for objective tumor evaluation.

ASSESSMENT OF TUMOR BURDEN

To assess objective response or future progression, it is necessary to estimate the overall tumor burden at baseline and use this as a comparator for subsequent measurements.

IDENTIFICATION OF TARGET AND NON-TARGET LESIONS

When more than one measurable lesion is present at baseline, all lesions up to a maximum of five lesions total (and a maximum of two lesions per organ) representative of all involved organs should be identified as target lesions and will be recorded and measured at baseline. This means that, for instances in which patients have only one or two organ sites involved, a maximum of two lesions (one site) and four lesions (two sites), respectively, will be recorded. Other lesions (albeit measurable) in those organs will be considered non-target lesions.

Target lesions should be selected on the basis of their size (lesions with the longest diameter) and be representative of all involved organs, but in addition should lend themselves to reproducible repeated measurements. It may be the case that, on occasion, the largest lesion does not lend itself to reproducible measurement, in which circumstance the next largest lesion that can be measured reproducibly should be selected.

Lymph nodes merit special mention since they are normal anatomical structures that may be visible by imaging even if not involved by tumor. As noted above, pathological nodes that are defined as measurable and may be identified as target lesions must meet the criterion of a short axis of ≥ 15 mm by CT scan. Only the short axis of these nodes will contribute to the baseline sum. The short axis of the node is the diameter normally used by radiologists to judge if a node is involved by solid tumor. Lymph node size is normally reported as two dimensions in the plane in which the image is obtained (for CT, this is almost always the axial plane; for MRI, the plane of acquisition may be axial, sagittal, or coronal). The smaller of these measures is the short axis. For example, an abdominal node that is reported as being 20 mm \times 30 mm has a short axis of 20 mm and qualifies as a malignant, measurable node. In this example, 20 mm should be recorded as the node measurement. All other pathological nodes (those with short axis \geq 10 mm

Alectinib—F. Hoffmann-La Roche Ltd

126/Protocol BO41929, Version 4

but < 15 mm) should be considered non-target lesions. Nodes that have a short axis of <10 mm are considered non-pathological and should not be recorded or followed.

All lesions (or sites of disease) not selected as target lesions (measurable or non-measurable), including pathological lymph nodes, should be identified as non-target lesions and should also be recorded at baseline. Measurements are not required. It is possible to record multiple non-target lesions involving the same organ as a single item on the Case Report Form (CRF) (e.g., "multiple enlarged pelvic lymph nodes" or "multiple liver metastases").

CALCULATION OF SUM OF DIAMETERS

A sum of the diameters (longest diameter for non–lymph node lesions, short axis for lymph node lesions) will be calculated for all target lesions at baseline and at each subsequent tumor assessment as a measure of tumor burden.

Measuring Lymph Nodes

Lymph nodes identified as target lesions should always have the actual short axis measurement recorded (measured in the same anatomical plane as the baseline examination), even if the node regresses to < 10 mm during the study. Thus, when lymph nodes are included as target lesions, the sum of diameters may not be zero even if complete response criteria are met, since a normal lymph node is defined as having a short axis of < 10 mm.

Measuring Lesions That Become Too Small to Measure

During the study, all target lesions (lymph node and non–lymph node) recorded at baseline should have their actual measurements recorded at each subsequent evaluation, even when very small (e.g., 2 mm). However, sometimes lesions or lymph nodes that are recorded as target lesions at baseline become so faint on CT scan that the radiologist may not feel comfortable assigning an exact measurement and may report them as being too small to measure. When this occurs, it is important that a value be recorded on the CRF, as follows:

- If it is the opinion of the radiologist that the lesion has likely disappeared, the measurement should be recorded as 0 mm.
- If the lesion is believed to be present and is faintly seen but too small to measure, a default value of 5 mm should be assigned and "too small to measure" should be ticked. (Note: It is less likely that this rule will be used for lymph nodes since they usually have a definable size when normal and are frequently surrounded by fat such as in the retroperitoneum; however, if a lymph node is believed to be present and is faintly seen but too small to measure, a default value of 5 mm should be assigned in this circumstance as well and "too small to measure" should also be ticked).

To reiterate, however, if the radiologist is able to provide an actual measurement, that should be recorded, even if it is <5 mm, and in that case "too small to measure" should not be ticked.

Measuring Lesions That Split or Coalesce on Treatment

When non–lymph node lesions fragment, the longest diameters of the fragmented portions should be added together to calculate the sum of diameters. Similarly, as lesions coalesce, a plane between them may be maintained that would aid in obtaining maximal diameter-measurements of each individual lesion. If the lesions have truly coalesced such that they are no longer separable, the vector of the longest diameter in this instance should be the maximum longest diameter for the coalesced lesion.

EVALUATION OF NON-TARGET LESIONS

Measurements are not required for non-target lesions, except that malignant lymph node non-target lesions should be monitored for reduction to <10 mm in short axis. Non-target lesions should be noted at baseline and should be identified as "present" or "absent" and (in rare cases) may be noted as "indicative of progression" at subsequent evaluations. In addition, if a lymph node lesion shrinks to a non-malignant size (short axis <10 mm), this should be captured on the CRF as part of the assessment of non-target lesions.

RESPONSE CRITERIA

CRITERIA FOR TARGET LESIONS

Definitions of the criteria used to determine objective tumor response for target lesions are provided below:

• Complete response (CR): Disappearance of all target lesions

Any pathological lymph nodes must have reduction in short axis to < 10 mm.

- Partial response (PR): At least a 30% decrease in the sum of diameters of all target lesions, taking as reference the baseline sum of diameters, in the absence of CR
- Progressive disease (PD): At least a 20% increase in the sum of diameters of target lesions, taking as reference the smallest sum of diameters at prior timepoints (including baseline)

In addition to the relative increase of 20%, the sum of diameters must also demonstrate an absolute increase of \geq 5 mm.

• Stable disease (SD): Neither sufficient shrinkage to qualify for CR or PR nor sufficient increase to qualify for PD

CRITERIA FOR NON-TARGET LESIONS

